#### **Study Drug Action Taken**

The site investigator will classify the study drug action taken with regard to the AE. The action taken will be classified according to the categories below:

- **Dose not changed:** study drug dose not changed in response to an AE
- **Dose reduced:** study drug dose reduced in response to an AE
- **Drug interrupted:** study drug administration interrupted in response to an AE

- **Drug withdrawn:** study drug administration permanently discontinued in response to an AE
- **Not applicable:** Action taken regarding study drug administration does not apply. “Not applicable” will be used in circumstances such as when the investigational treatment had been completed before the AE began and no opportunity to decide whether to continue, interrupt, or withdraw treatment is possible.

### ***Adverse Event Outcome***

An AE will be followed until the site investigator has determined and provided the final outcome or the participant has completed the study.

- **Recovered/resolved:** resolution of an AE with no residual signs or symptoms
- **Recovered/resolved with sequelae:** resolution of an AE with residual signs or symptoms
- **Not recovered/not resolved (continuing):** either incomplete improvement or no improvement of an AE, such that it remains ongoing
- **Fatal:** outcome of an AE is death. “Fatal” will be used when death is at least possibly related to the AE
- **Unknown:** outcome of an AE is not known (e.g. a subject lost to follow-up)

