## METHODS AND PROCEDURES

**Study Design:** Describe the research design, including a description of any new methodology and its advantage over existing methodologies.

A 14 week, randomized, double-masked, placebo controlled trial in 40 participants.

This study will be performed at the University of Vermont and Duke University. Two centers will facilitate recruitment, and improve generalizability of findings to inform any decision to proceed with a full-scale, appropriately powered multi-center trial.

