Drug return/ Pill counts				*	*		*
Assess for adverse events		*	*	*	*	*	*
Spirometry	*¥	* €				*€	*€
Forced oscillation	*	*				*	*
Lung Volumes	*						
Induced sputum	*					*‡	
Exhaled breath condensate	*	*					*
Exhaled nitric oxide	*	*					*
Methacholine Challenge		*^					*
Nasal lavage & nasal brush	*	*					*
Nasal strip	*	*				*	*
Asthma Control (ACT)	*	*		*	*		*
Marks AQLQ	*	*		*	*		*
ASUI	*						
Anthropometrics	*	*		*	*		*
Temperature	*	*					*
Blood pressure	*	*				*	*
Blood draw†	*	Fasting		Fasting	Fasting	Fasting	
Urine sample	*	*		*	*	*	*
Pregnancy test*	*	*		*	*	*	*
Follow-up phone call			*				
End of study questionnaire							*
Follow-up visit+	*	*				*	*

\*for women of child-bearing potential

¥V1 spirometry only will be performed pre and post bronchodilator

†fasting blood draw may be performed on a different day ( $\pm 7$  days of actual visit)

‡Induced sputum at V5 will be performed within 10 days prior to the other V5 procedures (induced sputum and methacholine cannot be done at same visit, both may cause bronchoconstriction)

^participants with a negative methacholine test will stop visit 2 early

†follow-up visits will be scheduled in the event that a lung test cannot be performed that day

€ spirometry is done as part of the induced sputum or methacholine procedure

∞Visit windows for the visits following visit 2 will be scheduled based off of the date the participant was randomized to study drug

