#### Visit 5a (duration 1.5 hours)

We will schedule the induced sputum prior to other study procedures (within 10 days of V5). We will assess for any adverse events, measure blood pressure, perform forced oscillation, obtain spontaneous sputum or perform the induced sputum procedure, review concomitant medications, and obtain an interim medical history. We will insert a nasal strip for sample collection. We will collect urine for research. Women of childbearing potential will perform a urine pregnancy test. Participants will have fasting blood drawn for

blood glucose, CBC w/ differential, CMP, and collection of serum and plasma for research (this may also be scheduled within 7 days per participant preference).

Visit 5b (duration 3 hours)

We will collect and review diary cards and assess adherence to study medication (by pill count). We will collect all remaining study drug. We will perform nasal lavage, collect nasal cells via nasal brush, measure blood pressure, temperature, obtain weight, and hip and waist circumference. Participants will perform spirometry. We will insert a nasal strip for sample collection. We will collect urine for research. Women of childbearing potential will perform a urine pregnancy test. We will perform a methacholine challenge test with forced oscillation (measuring response by both FEV1 and forced oscillation). If we are unable to obtain sputum from the participant at visit 5a we will see if the participant is able to produce sputum spontaneously during pulmonary function testing. We will collect exhaled breath condensate and exhaled nitric oxide. Participants will complete questionnaires about asthma control and asthma quality of life, and an end of study participant questionnaire.

Additional visit:

Some participants may be asked to return for an additional visit if some of the tests were not completed at the regular scheduled visits or for unexpected events. This additional visit may involve spirometry, a methacholine challenge, or induced sputum depending on the need for the specific participant. The participant's blood pressure will be assessed if the methacholine challenge or induced sputum need to be performed. In addition, women of childbearing potential will be required to undergo a urine pregnancy test prior to testing.

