An adverse event (AE) is any unanticipated or unintended medical occurrence or worsening of a sign or symptom (including any clinically significant abnormal laboratory finding as determined by the study physician) or disease in a study participant, which does not necessarily have a causal relationship with the study condition, procedures or study agent(s), that occurs after the informed consent is obtained.

Pre-existing conditions or illnesses which are expected to exacerbate or worsen are not considered adverse events.

*Definition of a Serious Adverse Event (SAE)*

Serious Adverse Event (SAE): A Serious Adverse Event is defined as an AE meeting one of the following outcomes:

- Death during the period of protocol defined surveillance
- Life Threatening Event (defined as a participant at immediate risk of death at the time of the event)
- Inpatient hospitalization or prolongation of existing hospitalization during the period of protocol defined

surveillance

- Results in congenital anomaly or birth defect
- Results in a persistent or significant disability/incapacity

Any other important medical event that may not result in one of the above outcomes, may be considered a serious adverse experience when, based upon appropriate medical judgment, the event may jeopardize the participant and may require medical or surgical intervention to prevent one of the outcomes listed above

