## **Blinding and unblinding**

### **1. Blinding:**

- All subjects (including caregivers/companions) and site personnel (including the investigator and study team) will be blinded to the treatment code.
- Individuals who may be unblinded include only the following:
  - Any site personnel for whom this information is important to ensure the safety of the subject in the event of a life-threatening medical emergency
  - Any site personnel for whom this information is important to ensure the safety of the subject and her fetus in the event of a pregnancy
  - Biostatistician preparing the final randomization list
  - MIMDA IDS pharmacy personnel

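### Adverse event follow-up may stop at study completion with no routine safety contact after V5b, leaving late events, open SAE outcomes and pregnancy outcomes without active follow-up

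*Combined protocol and SAP*

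**What the plan says.** The follow-up rule is in the Adverse Event Outcome section: "An AE will be followed until the site investigator has determined and provided the final outcome or the participant has completed the study". It covers every adverse event (AE), whatever its grade or seriousness. One of the outcome codes that follow begins "Not recovered/not resolved (continuing" and is for events still ongoing.

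The study is described as "A 14 week, randomized, double-masked, placebo controlled trial in 40 participants". The visit table puts V5b at week 12, plus or minus 10 days, and visits after V2 are "scheduled based off of the date the participant was randomized to study drug". At V5b, "We will collect all remaining study drug" and "We will perform a methacholine challenge test with forced oscillation"; the nasal brush and the end-of-study questionnaire fall at the same visit. The Unmasking section has participants told their assignment at the end of V5b.

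The definition of an SAE includes "Results in congenital anomaly or birth defect". For death and hospitalisation it refers to a protocol-defined surveillance period, whose length is not given in the available text. The Blinding section allows unblinding to "ensure the safety of the subject and her fetus in the event of a pregnancy".

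**The concern.** A safety record normally runs somewhat past the last exposure, and SAEs and pregnancies are normally followed to an outcome. Here the follow-up rule can be satisfied by study completion alone, and the schedule has no routine contact after the visit at which drug is handed back. The final visit also includes a bronchial challenge and a nasal procedure.

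Three kinds of information are at stake: new events after the last dose or after the V5b procedures, the outcomes of SAEs still open at completion, and the outcomes of pregnancies begun on study. This matters in a small trial under an IND, which uses 40 mg per day against a recommended supplement dose of 20 mg and cites tolerability as one reason for its duration. The Stopping rules act on two SAEs definitely or probably related, or three possibly related, so a single late SAE that nobody asks about could change the count while others are still being treated.

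**Working it through.** **1. Study length.** V1 is at week -2 and V5b at week 12: 12 - (-2) = 14 weeks, which reproduces the stated length. The stated length therefore contains no period after V5b.

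**2. Timing of V5b.** Week 12 is day 84 from randomisation. The window gives 84 - 10 = 74 to 84 + 10 = 94 days (10.6 to 13.4 weeks). For a participant dosed up to V5b, scheduled off-drug follow-up is 0 days.

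**3. The two methacholine challenges compared.** The call after V2 is at day 3 with a further 3 days allowed, so day 3 to 6, and it asks about AEs. No call follows V5b. With 40 randomised participants there are 40 + 40 = 80 planned challenges, and the 40 at V5b have no later scheduled AE check. If the 10% drop-out allowed for in the Sample size section occurs, the V5b number is 40 x 0.9 = 36. The visit table marks an AE check at V5b, but the V5b narrative does not mention it, and neither says that it comes after the challenge.

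**4. The last safety bloods.** V5a is 1 to 10 days before V5b, and its fasting draw (including CBC and CMP) may be up to 7 days either side of the visit. If V5a is k days before V5b, the latest draw is 7 - k days after V5b. For k = 1 that is 6 days after V5b, or day 94 + 6 = 100 at the latest. For k = 1 to 6 the draw can fall after V5b. The AE definition counts an abnormal result that the study physician considers clinically significant, so the plan can generate an AE after its last scheduled AE check.

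**5. Pregnancy.** The documents give no gestation figures. Assume birth 24 to 38 weeks after conception, and conception 0 to 3 weeks before V2 and missed by the V2 test. At the latest V5b, time since conception is 94/7 + 0 = 13.4 to 94/7 + 3 = 16.4 weeks. The gap from V5b to birth is then 24 - 16.4 = 7.6 weeks at the shortest and 38 - 13.4 = 24.6 weeks at the longest. Later conception or an earlier V5b widens it. No birth falls inside scheduled follow-up under any of these assumptions, and a pregnancy first found by the V5b test has no scheduled follow-up at all.

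**6. Participants who leave early.** Pregnancy is an exclusion criterion, and under Withdrawal Procedures a newly met exclusion criterion may lead to discontinuation from the study. Those who withdraw are asked only for questionnaires. Follow-up of a pregnancy could therefore end before V5b.

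**The case against.** The strongest reply is that following an event is different from detecting and reporting it. A reader might infer that SAEs still open at V5b are lost to reporting and to the stopping count. The documents do not support that: such an SAE has already occurred, the Reporting section runs from the event or from awareness of it, and the Stopping rules count events without waiting for resolution. This part of the reply stands.

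A reader might also infer that a birth defect or other late event could never be recorded. That is too strong. The AE definition starts at consent and has no end date, the Study Drug Action Taken section has a code for events that begin after treatment is complete, and the investigators may report any event they judge reportable with no cut-off. These routes depend on someone hearing of the event, and nothing after V5b is designed to ask.

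Nor is off-drug follow-up zero for everyone. The Treatment termination section asks those taken off treatment early to keep attending visits until completion. The visit table and the additional-visit paragraph also allow extra contact for missed tests or unexpected events, though this is contingent, untimed and not tied to AE resolution. Study completion is nowhere defined as V5b; that is inferred from the schedule. The word "or" in the rule does not say which condition governs.

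Two further points have some weight. The challenge is done under close monitoring with a bronchodilator at hand, and the documents describe no delayed harm from it. MitoQ is described as well tolerated at up to 80 mg per day for 12 months. These lower the expected yield of a late check but do not supply one.

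Finally, the text immediately before the AE definition was not available. It may define the surveillance period or a pregnancy rule. If it does, it needs a cross-reference in the Adverse Event Outcome section, which carries no exception.

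**Conclusion.** The point holds as an inexpensive improvement to safety follow-up. In the available text, follow-up of every AE ends at final outcome or study completion, and no routine safety contact is scheduled after V5b (day 74 to 94). For participants dosed up to V5b:

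- new events after the last dose or the V5b procedures are captured only by spontaneous report or a contingent visit;
- SAEs open at completion may be left as continuing;
- the last CBC and CMP can be drawn up to 6 days after V5b;
- the birth-defect criterion cannot be met through scheduled follow-up.

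What is at risk is the outcome of known SAEs and the detection of new late ones, not the reporting of SAEs already known. The documents give no basis for an expected number of missed events. The conclusion assumes that completion means V5b for participants who finish on schedule, that the unavailable text sets no overriding rule, and, for pregnancy, the gestation range shown. The primary efficacy analysis is unaffected.

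**What to change.** - Amend the Adverse Event Outcome section so that SAEs, related AEs of grade 3 or higher, clinically significant laboratory abnormalities and any on-study pregnancy are followed to resolution, stabilisation or outcome, regardless of study completion.
- Define study completion and the surveillance period used in the SAE definition, and reconcile both with the Adverse Event Outcome, V5b, additional-visit and Blinding text.
- Add one AE telephone call after V5b, in the existing ten-minute format. Timing it after the latest permitted V5a draw would also cover those results.
- State that SAEs learned of after V5b enter the existing Reporting route and the existing Stopping rules count.

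The cost is a protocol amendment and at most 40 x 10 = 400 minutes of calls (under 7 staff hours; 36 x 10 = 360 minutes with 10% drop-out), plus follow-up of the few open cases. No new procedure or staff is needed. One limitation is that participants learn their assignment at the end of V5b, so later self-reports would not be blinded and should be presented separately from on-treatment events.

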### **Reporting**

Adverse event reporting for this protocol will be as follows:

- The PI's will submit a completed serious adverse event report to the IRB, NIH and Chair of the DSMP within 48 hours after any potentially life-threatening (grade 4) serious adverse event that is possibly, probably or definitely related to the study.
- The PI's will submit a completed serious adverse event report to the IRB, NIH and Chair of the DSMP within 48 hours after becoming aware of any Grade 3 (severe) adverse event that is possibly, probably or definitely related to the study.
- The PI's will report within 15 days on any other event or condition regardless of grade, which in their judgment represents an event reportable to the IRB, NIH and DSMP.
- A summary of all adverse events will be reported to the DSMP, NIH and IRB annually.

### **Reporting Mechanisms of IRB actions to NHLBI**

Routine IRB actions will be summarized in annual reporting to the IRB.

IRB actions that involve significant safety issues will be reported to NHLBI within 15 days of the action.

***Withdrawal Procedures:*** Define the precise criteria for withdrawing subjects from the study. Include a description of study requirements for when a subject withdraws him or herself from the study (if applicable).

Participants may withdraw at any-time, we will ask the participant to consider completing questionnaires regarding asthma control, and quality of life and end of study questionnaire if they withdraw prior to the end of the study.

A study participant will be discontinued from the study for:

- Any clinical adverse event, clinically significant laboratory abnormality, intercurrent illness, other medical condition or situation occurs such that continued participation in the study would not be in the best interest of the participant in the opinion of the site investigator.
- Development of any exclusion criteria may be cause for discontinuation.
- Stops corresponding with study staff team, i.e., “lost to follow-up”. Participants will be contacted at least three times by either e-mail or phone. These contact attempts will be recorded by study personnel. If the participant does not respond after the third attempt, they may be withdrawn from the study and considered “lost to follow-up”.

## **Stopping rules**

During the study period if there is a primary reason to halt this study related to concerns regarding safety we will stop the protocol in the event of the following.

### **1. Serious Adverse Events**

The protocol will be stopped for two serious adverse events that are definitely or probably related to the study protocol. The protocol will be stopped in the event that there are three events that are thought to be possibly related to the study protocol.

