**Not Applicable**

Participants will stay on their usual asthma medications per their asthma care provider. There are no medications specifically targeting obese patients with asthma. The alternative is not to participate in this study.

***Data Safety and Monitoring:*** The specific design of a Data and Safety Monitoring Plan (DSMP) for a protocol may vary extensively depending on the potential risks, size, and complexity of the research study. For a minimal risk study, a DSMP could be as simple as a description of the Principal Investigator's plan for monitoring the data and performance of safety reviews or it could be as complex as the initiation of an external, independent Data Safety and Monitoring Board (DSMB). The UVM/UVM Medical Center process for review of adverse events should be included in the DSMP.

The DSMB will include 3 physician scientists (not from the University of Vermont or Duke University) who are active in asthma research.

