#### **Relationship Assessment**

For all collected AEs, the site investigator who examines and evaluates the subject will determine the adverse event's causality based on temporal relationship and his/her clinical judgment. The degree of certainty about causality will be graded using the categories below:

- **Definitely Related:** There is clear evidence to suggest a causal relationship, and other possible contributing factors can be ruled out. The clinical event, including an abnormal laboratory test result, occurs in a plausible time relationship to study visit.
- **Probably Related:** There is evidence to suggest a causal relationship, and the influence of other factors is unlikely. The clinical event, including an abnormal laboratory test result, occurs within a reasonable time sequence to administration of the study visit, is unlikely to be attributed to concurrent disease or other drugs or chemicals.
- **Possibly Related:** There is some evidence to suggest a causal relationship. However, the influence of other factors may have contributed to the event (e.g., the subject's clinical condition, other concomitant events).
- **Unlikely:** A clinical event, including an abnormal laboratory test result, whose temporal relationship to study visit makes a causal relationship improbable (e.g., the event did not occur within a reasonable time) and in which other drugs or chemicals or underlying disease provides plausible explanations (e.g., the subject's clinical condition, other concomitant treatments).
- **Unrelated:** The AE is completely independent of study, and/or evidence exists that the event is definitely related to another etiology. There must be an alternative, definitive etiology documented by the clinician.
- **Expected Events Related to Disease Process:** Expectedness refers to the awareness of adverse events related to study.

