### **2. Adverse Events**

For adverse events that are not within the category of serious adverse events, the protocol will be stopped in the events that are 4 adverse event of grade 3 category that are thought to be definitely or probably related to the study protocol. The study will not be stopped for grade 2 or lower adverse events.

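### The serious adverse event stopping rule has no combined count: one probably related plus two possibly related events do not stop the trial, but three possibly related events do

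*Combined protocol and SAP*

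**What the plan says.** The stopping rules section of the protocol has two items. Item 1 (Serious Adverse Events) contains two separate limbs. The first reads: "The protocol will be stopped for two serious adverse events that are definitely or probably related to the study protocol". The second requires a stop if "there are three events that are thought to be possibly related to the study protocol". Neither says how events of different grades are to be added together.

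The grades are defined under Relationship Assessment, which states: "The degree of certainty about causality will be graded using the categories below". It then lists Definitely, Probably and Possibly Related as separate entries, each with its own criteria.

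Item 2 (Adverse Events) sets a threshold of four grade 3 events that are definitely or probably related. It opens by confining itself to non-serious events: "For adverse events that are not within the category of serious adverse events".

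Under Data Safety and Monitoring, an external board is named: "The DSMB will include 3 physician scientists". The Reporting section requires 48-hour reports for grade 3 and grade 4 events at any of the three related grades.

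**The concern.** A safety rule should never become less protective as the evidence of harm grows. Here it can. Suppose three SAEs have occurred, all graded possibly related: the second limb is met and the trial stops. Now suppose one of the three is graded probably related instead. The first limb has one event of the two it needs, the second has two of three, and the trial continues.

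What is at stake is one further participant with a related SAE before the mandatory stop takes effect, in a trial of 40 people.

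A smaller point in the same sentence: the second limb says events without repeating the word serious, so only the heading limits it to SAEs.

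**Working it through.** **Which reading the text supports.** The second limb could mean events graded exactly *possibly*, or events graded *possibly* or higher. Three places bear on this:

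- Relationship Assessment makes the three grades separate categories.
- The Reporting section lists all three grades when it pools them: "that is possibly, probably or definitely related to the study". Adverse Event Outcome writes a floor out in words: "death is at least possibly related to the AE". The latter concerns whether a death is related to an adverse event, so it is the weaker parallel.
- The first limb of the rule names two grades where two are meant. The second limb names one.

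Together these favour the exact-grade reading, which the rest of the check uses.

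**Enumeration.** Let *a* be the number of definite or probable SAEs and *b* the number of possible SAEs.

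- As written: stop if *a* ≥ 2 or *b* ≥ 3.
- Combined count: stop if *a* ≥ 2 or *a* + *b* ≥ 3.

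| *a* | *b* | As written | Combined |
|---|---|---|---|
| 0 | 0, 1 or 2 | continue | continue |
| 0 | 3 | stop | stop |
| 1 | 0 or 1 | continue | continue |
| 1 | 2 | **continue** | **stop** |
| 1 | 3 | stop | stop |
| 2 | any | stop | stop |

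Only (1,2) differs. It is also the only state that continues although moving one event down a grade, to (0,3), would stop. Three related SAEs can fall in four patterns, (3,0), (2,1), (1,2) and (0,3), and one of the four escapes. From (1,2) the next related SAE gives (2,2) or (1,3), and both stop.

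**Chance of landing there.** The plan attaches no operating characteristic to the rule, so there is no stated figure to reproduce. Inputs: n = 40 randomized (Number of Subjects); per-participant rates q₁ (definite or probable) and q₂ (possible), which are assumptions; and at most one related SAE per participant, also assumed. The gap between the two rules is

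P(1,2) = 40·q₁ · C(39,2)·q₂² · (1 − q₁ − q₂)³⁷, with C(39,2) = 741.

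At q₁ = 1% and q₂ = 2%: 0.4 × 741 × 0.0004 × 0.97³⁷ = 0.11856 × 0.3240 = 0.0384.

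The chance of a stop as written is one minus the sum over the six continuing states (0,0), (0,1), (0,2), (1,0), (1,1), (1,2):

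1 − (0.2957 + 0.2439 + 0.0981 + 0.1219 + 0.0981 + 0.0384) = 0.1039.

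Adding 0.0384 gives 0.1423 for the combined count (to rounding). The other assumed rates follow the same way:

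| q₁ / q₂ | As written | Combined | Gap |
|---|---|---|---|
| 0.5% / 1% | 2.5% | 3.3% | 0.85 points |
| 1% / 2% | 10.4% | 14.2% | 3.8 points |
| 1% / 4% | 26.3% | 33.4% | 7.1 points |
| 2% / 4% | 36.7% | 46.3% | 9.6 points |

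**Given that a third related SAE occurs.** Let *p* be the share of related SAEs graded definite or probable. If the trial is still running after two related SAEs, they were not both definite or probable, which has probability 1 − *p*². The third event then fails to trigger with probability 3*p*(1 − *p*)² / (1 − *p*²):

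- *p* = 0.2: 0.384 / 0.96 = 0.40
- *p* = 1/3: 0.444 / 0.889 = 0.50
- *p* = 0.5: 0.375 / 0.75 = 0.50

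These conditional figures need their denominator. Three or more related SAEs occur in about 2% of trials at 0.5%/1% and about 12% at 1%/2%.

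**The case against.** The strongest reply is that relatedness is an ordered scale of certainty. A probably related SAE more than meets the evidence needed for *possibly*, so counting it towards three is natural and may be what the authors meant. The drafting in this part of the protocol is loose, so fine differences of wording are thin evidence of intent. That is fair as far as it goes: intent cannot be settled from the text. But the exact-grade reading is the better supported one, and a mandatory halting rule should not depend on which reading a site or the board adopts. If a floor was meant, writing it down costs nothing.

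The second reply is that the harm is small. It is a delay of one event, an external board exists, related grade 3 and 4 events are reported within 48 hours, individual participants can be withdrawn on safety grounds, and nothing visible bars an earlier stop. All of this stands and limits the weight of the point. The text between the board's composition and the adverse event definition was not available, so any halting discretion given there is not assessed. Such discretion would soften the consequence without changing the mandatory wording.

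Third, the probabilities rest on assumed rates. The top of the range needs 40 × 0.06 = 2.4 expected related SAEs, and the protocol describes the supplement as well tolerated. This also stands, which is why a range is given. The missing word serious is minor, since the heading and the opening of item 2 divide the two kinds of event clearly enough.

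**Conclusion.** The concern holds. On the more natural reading of the text, a mandatory SAE stopping rule gives an inverted result in exactly one state: one definite or probable SAE with two possible SAEs. Item 2 does not catch that state because it excludes SAEs. The consequence is a delay of one related SAE. In absolute terms the rule misses about 1 to 10 percentage points of mandatory stops, under assumed rates from 0.5%/1% to 2%/4%, 40 participants and at most one related SAE each. The enumeration needs none of these rate assumptions; it depends only on the exact-grade reading. The rule should be corrected, because it concerns participant safety and the repair is simple.

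**What to change.** Reword only the second limb of item 1, so that the protocol stops once three serious adverse events have been graded at least possibly related, meaning definitely, probably or possibly. This makes the rule consistent across grades and supplies the missing word serious. Both thresholds, two and three, stay as they are, and item 2 needs no change.

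The cost is one sentence and a modestly higher chance of a mandatory stop: 3.8 points at 1%/2% and 9.6 points at 2%/4%. Those extra stops are not specific to MitoQ harm, because the rule counts events related to the study protocol in both arms under blinding, including events from study procedures such as methacholine challenge. They do, however, arise only where attribution is stronger than in a pattern that already stops the trial.
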